7.6. Ultrasound-Guided Injection of Study Drug

AA4500 0.58 mg and placebo will be administered in a volume of 1 mL after reconstitution with sterile diluent (0.9% sodium chloride containing 0.03% calcium chloride) according to the instructions in the Pharmacy Manual.

Prior to the injection procedure, the investigator, the assistant, ultrasound machine, and all necessary supplies should be prepared and in place. The subject should be in the supine position. The ultrasound machine should be placed at the head of the subject. The sterile ultrasound probe cover should be placed on the ultrasound probe. The sterile ultrasound transducer gel should be easily accessible.

- Once the anesthetic effect has been achieved, the injection site area should once more be prepped with an appropriate antiseptic such as ChloroPrep® (chlorhexidine) or Betadine®. The injection site of the local anesthetic should be visible.

- The affected arm should be passively externally rotated to the subject's level of pain tolerance with the elbow at the side (against the body) and flexed to 90°. **If the affected arm cannot be passively externally rotated to at least the neutral position, the injection cannot be administered.** Pendulous breasts may be retracted.
- The assistant should apply sterile ultrasound transducer gel and place the sterile ultrasound probe 2 cm to 5 cm cephalad to the previously marked injection site. The affected shoulder joint and anterior capsule should be visible on the ultrasound screen. These anatomic landmarks should be identified. The ultrasound image of the affected shoulder joint and the anterior capsule should be visible to the investigator throughout the entire injection procedure.
- The investigator will handle the metal shaft of the spinal needle with one hand ("needle" hand) and the syringe containing reconstituted study drug with the other hand ("syringe" hand). Sterile gloves will be needed to allow the "needle" hand to remain sterile throughout the injection procedure. The "needle" hand will be the hand guiding the needle tip into the same skin puncture hole previously made by the anesthetic needle.
- With his/her "syringe" hand, the investigator should pick up the previously prepared syringe of the reconstituted study drug with the attached 22-gauge spinal needle. The assistant should then carefully remove the protective plastic covering of the spinal needle.
- With his/her "needle" hand, the investigator should help guide the spinal needle as needed through the puncture site that was created by the 20-gauge local anesthetic needle. This step should be performed slowly and with care under ultrasound guidance.
- When the investigator feels the resistance of the pathologically thickened shoulder joint capsule, a bending or flexing of the spinal needle will usually be appreciated. He or she should stop further advancement of the needle. At this time, the location of the needle tip should be confirmed by ultrasound as being extra-articular. The tip of the spinal needle should stay outside of the anterior shoulder joint capsule. Do not allow the spinal needle to penetrate the anterior shoulder capsule or joint. If it is suspected that the spinal needle has penetrated the anterior shoulder joint capsule, do not inject study drug. Reposition the spinal needle tip.
- When the proper position of the spinal needle is confirmed, inject the entire dose of study drug. After study drug is injected, remove the spinal needle. Place an adhesive bandage on the injection site. All needles and sharps in this clinical trial should be handled using appropriate guidelines and in accordance with the investigator's institution.

- Following the injection of study drug, the subject should remain supine and be directly observed for 20 minutes. Thereafter the subject should be observed in accordance with the instructions as outlined in Section 7.14.7.

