^a 4 hours before injection and approximately 15, 30 and 45 minutes after injection, and before discharge.

^b The unaffected shoulder will also be examined at screening.

^c Subjects may receive up to a total of three injections; each injection separated by a minimum of 21 days.

NOTE: Subjects who are not eligible for Injection 2 and/or Injection 3 (eg, successfully treated or safety concern) will have follow-up visits on Day 43 and Day 64. Subjects who are not eligible for Injection 2 and/or Injection 3 will not be required to have a study visit on Day 29 and/or Day 50, respectively.

Subjects who are not eligible for Injection 2 because of a safety concern may receive Injection 3 at the discretion of the investigator.

All subjects will have a final follow-up visit on Day 95.

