7.14.7. Vital Signs

During the screening period, each subject will have blood pressure (systolic/diastolic), respiratory rate, and radial pulse assessed after he/she has been seated upright for at least 5 minutes. Body temperature will also be recorded.

On each injection day, vital signs will be assessed after the subject has been seated upright for at least 5 minutes as shown in Table 4.

Table 4: Vital Signs Measurements – Injection Days

Time point Relative to Injection	Blood Pressure, Respiratory Rate, Radial Pulse	Body Temperature
Up to 4 hours before	X	X
Approximately 15 minutes after	X	
Approximately 30 minutes after	X	
Approximately 45 minutes after	X	
Before discharge from the unit	X	X

Follow-up vital sign measurements, including blood pressure (systolic/diastolic), respiratory rate, and radial pulse, will be assessed after the subject has been seated upright for at least 5 minutes on Days 8, 29, 50, 64, and at the Day 95 follow-up visit.

NOTE: blood pressure should be taken on the non-treated arm.

7.14.8. 12-Lead Electrocardiogram

During the screening period, subjects will have a resting 12-lead electrocardiogram (ECG). A qualified physician will interpret, sign, and date the ECGs. Electrocardiogram assessments must be ‘within normal limits’ or interpreted as ‘abnormal, not clinically significant’ for the subject to be included in the study. ECG findings will be documented as normal; abnormal, clinically significant; or abnormal, not clinically significant. The investigator or qualified designee must sign and date the ECG, thereby acknowledging review of ECG results.

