10.1.3. Safety

The following variables are safety endpoints.

1. Adverse events: Mapped to preferred term using the Medical Dictionary for Regulatory Activities (MedDRA)
2. Change from screening visit in vital signs
3. Change from screening visit in laboratory tests

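### The 15-minute post-injection vital-sign reading cannot meet both posture rules, and injection-day change is referred to screening although a same-day pre-injection reading is collected

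*Protocol*

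**What the plan says.** **Posture and timing.** Section 7.6 ends the injection procedure with "Following the injection of study drug, the subject should remain supine and be directly observed for 20 minutes". It continues: "Thereafter the subject should be observed in accordance with the instructions as outlined in Section 7.14.7". Section 7.14.7 says that on injection days "vital signs will be assessed after the subject has been seated upright for at least 5 minutes as shown in Table 4". The first post-injection row of Table 4 is "Approximately 15 minutes after", followed by rows at about 30 and 45 minutes and before discharge. Table 1 footnote a repeats the schedule: "approximately 15, 30 and 45 minutes after injection, and before discharge". Section 7.7 lets a subject leave after 45 minutes if, among other conditions, vital signs stayed stable over that period, and it refers to Section 7.14.7 for the readings.

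**Reference for change.** Section 10.1.3 lists the safety endpoint as "Change from screening visit in vital signs". Section 10.2.2 summarises actual values and change from baseline by arm at each visit. Section 10.1.2 defines baseline for efficacy parameters only. Table 4 also schedules a reading on every injection day at "Up to 4 hours before", but no section names it as the reference for post-injection change.

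**The concern.** A site following Section 7.6 cannot also follow Section 7.14.7 at the 15-minute reading. It has three ways out: take the reading supine, sit the subject up during the supine period, or take the reading late. Each departs from one instruction, and the protocol does not say which. If the reading is supine, it stands next to seated pre-injection, 30-minute and 45-minute readings. Posture can itself shift blood pressure and pulse, so a posture change within the window could imitate or mask a change in a subject whose discharge depends on stability.

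The context gives the reading some weight. Section 3.4.1 says that an antibody response to this foreign protein is expected in all subjects and that serious allergic reaction has been reported after the marketed product.

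The second part concerns the summary. The 15-, 30- and 45-minute readings exist to show what happens shortly after an injection. Change from a screening reading taken weeks earlier also carries visit-to-visit variation, although a closer reference is already collected.

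**Working it through.** The protocol gives no figure to reproduce here. The check is a timeline, a lag count and a sensitivity range.

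**1. Feasibility of each timed reading**

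Inputs: supine from minute 0 to 20 (Section 7.6); at least 5 minutes seated before each reading (Section 7.14.7); readings at about 15, 30 and 45 minutes (Table 4, Table 1 footnote a).

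Latest time to be seated = reading time − 5. The reading is feasible if this is at or after minute 20.

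| Reading | Latest time to sit up | Supine period ends | Feasible |
|---|---|---|---|
| 15 min | 15 − 5 = 10 | 20 | No, 10 minutes short |
| 30 min | 30 − 5 = 25 | 20 | Yes |
| 45 min | 45 − 5 = 40 | 20 | Yes |

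The discharge reading falls after the 45-minute observation period, so it is also feasible.

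Earliest reading that meets both posture rules = 20 + 5 = minute 25. That is 25 − 15 = 10 minutes after the scheduled time and 30 − 25 = 5 minutes before the next reading.

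There is a second clash of the same kind. Section 7.6 hands over to Section 7.14.7 only after the 20 minutes, but Section 7.14.7 contains a reading due at minute 15.

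**2. How many readings**

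One per injection and up to 3 injections give at most 3 per subject. With 300 planned subjects the ceiling is 300 × 3 = 900. The actual number would be lower, because Injections 2 and 3 depend on the retreatment guidelines and investigator discretion (Section 7.11) and Section 10.3 assumes 20% dropout.

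**3. Age of the screening reference**

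Inputs: screening at most 28 days before Injection 1 (Section 7.13.2); injections on nominal Days 1, 22 and 43.

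- Injection 1: up to 28 days
- Injection 2: up to 28 + 21 = 49 days
- Injection 3: up to 28 + 42 = 70 days (43 days if screening was on Day −1)

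The same-day reading is at most 4 hours old before the injection.

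**4. Effect on the noise of the summarised change**

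The protocol gives neither a standard deviation nor correlations for vital signs, so everything in this step is an assumption.

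With equal SD σ at both times and correlation r, SD of change = σ√(2(1 − r)). The reduction from using the same-day reference is 1 − √[(1 − r_same) / (1 − r_weeks)], in which σ cancels. The SDs below use σ = 15 mmHg for systolic pressure.

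| r same day | r across weeks | SD of change, same day | SD of change, screening | Reduction |
|---|---|---|---|---|
| equal | equal | equal | equal | 0% |
| 0.7 | 0.6 | 15√0.6 = 11.6 | 15√0.8 = 13.4 | about 13% |
| 0.8 | 0.5 | 15√0.4 = 9.5 | 15√1.0 = 15.0 | about 37% |

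The same-day reference is less noisy whenever readings hours apart correlate more strongly than readings weeks apart.

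**The case against.** **On the posture conflict.** Table 4 says approximately, which allows some latitude. It does not plausibly stretch 15 minutes to 25, which is closer to the next scheduled reading than to its own. The conflict therefore stands, but it is narrow. A reader might infer that the whole post-injection vital-sign schedule is unworkable. It is not: only the 15-minute reading conflicts.

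A reader might also infer that the earliest check for an allergic reaction is compromised. Sections 7.6 and 7.7 provide direct observation for the first 20 minutes, and Section 7.7 assigns it to staff skilled in managing acute allergic reactions. The 15-minute reading is the first post-injection vital-sign measurement, not the first safeguard.

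**On the reference.** It is tempting to say that the screening reference hides acute reactions. The documents do not support this. The discharge condition is stability within the 45-minute period and does not use the screening value. Section 8.1.1 captures vital-sign changes as adverse events when, among other triggers, the investigator judges them clinically significant or they need treatment. The Section 10.2.2 summary is descriptive and includes actual values. Both arms share the same blinded schedule and the same rule, so extra noise does not favour either arm.

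A statistical analysis plan that is not shown could also add a change from the pre-injection reading, and a screening reference is conventional for visit-level change. These points reduce the weight of this part. They do not remove it: Section 10.1.3 names the screening visit explicitly, so this is a stated choice and not a detail left open.

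**Conclusion.** The contradiction is certain and rests on the protocol's text alone. Section 7.6 and Section 7.14.7 with Table 4 cannot both be followed at the 15-minute reading; the shortfall is 10 minutes at every injection. At most three readings per subject are affected, and 900 is only a ceiling. The consequence is a likely mix of postures inside the 45-minute stability window. How sites would resolve the conflict is unknown.

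The screening reference is a weaker, separate point. It makes the descriptive summary of acute change noisier, by anything from 0% to about 37% in SD of change over the assumed correlations. The upper figure belongs to one assumed pair and should not be read as an established loss. Likewise, the lag at Injection 3 is up to 70 days, not 70 days for everyone.

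Neither part affects the primary endpoint, power or type I error. Both deserve correction because the remedy is cheap and the readings concern safety.

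**What to change.** - Reconcile Section 7.6, Section 7.14.7 with Table 4, and Table 1 footnote a, so that a single posture and a single time apply to the first post-injection reading. Which clinical rule should prevail is for the sponsor and investigators to decide.
- Record posture on the CRF for each injection-day reading.
- In Sections 10.1.3 and 10.2.2, summarise change at the 15-, 30-, 45-minute and discharge readings from that injection day's pre-injection reading. Keep screening as the reference for non-injection visits.

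Cost: a clarifying amendment, one CRF field and one derivation. No new measurements are needed, because the pre-injection reading is already scheduled at every injection.

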7.7. Care Procedures After Injection

To evaluate the subject for possible immediate immunological adverse events, the subject will remain in direct observation of medical personnel who are skilled in the management of acute allergic reactions for the first 20 minutes after receiving an injection of study drug (see Section 7.6). A subject may be discharged from the study unit after a 45-minute observation period provided:

- The subject exhibits no sign of an immunological or other clinically significant systemic or local adverse event
- The subject's vital signs have remained stable throughout the 45-minute observation period (see Section 7.14.7)

Before discharge, the subject will be instructed to limit movement of his/her treated shoulder for 10 to 12 hours after injection of study drug. The investigator or qualified designee will apply a sling to the treated shoulder within 4 hours after injection. The sling will serve as a reminder to the subject to limit movement of the treated shoulder. Subjects will be instructed to remove the sling before sleeping and to inspect the treated shoulder for edema, sensation, and movement. The subject will be instructed to contact the investigator immediately if any problems are noticed.

Additionally, subjects will be instructed **NOT** to lift or carry any heavy objects for at least 8 weeks after each injection of study drug.

7.8. Identity of Investigational Product

The components of AA4500 are 0.9 mg of collagenase clostridium histolyticum and 0.5 mg of hydrochloric acid, 18.5 mg of sucrose, and 1.1 mg of tromethamine in a lyophilized cake.

The components of placebo for AA4500 are 0.5 mg of hydrochloric acid, 18.5 mg of sucrose, and 1.1 mg of tromethamine in a lyophilized cake.

The components of the sterile diluent are: 0.03% calcium chloride in 0.9% sodium chloride. Only sterile diluent supplied by Auxilium Pharmaceuticals, Inc. will be used.

7.9. Packaging and Labeling

Sterile vials of lyophilized study drug and sterile diluent will be provided to the investigator by Auxilium Pharmaceuticals, Inc. Each kit will contain 1 vial of lyophilized study drug and 1 vial of sterile diluent.

7.10. Storage and Disposition of Study Drug Supplies

Study drug and sterile diluent must be kept in a refrigerator (2°-8°C) with locked access. The reconstituted solution can be kept at room temperature (20° to 25°C/68° to 77°F) for up to one hour or refrigerated at 2° to 8°C (36° to 46°F) for up to 4 hours prior to administration.

All unused clinical supplies will be stored at controlled, refrigerated temperature, in an appropriate, secure place until used or returned to Auxilium Pharmaceuticals, Inc. The investigator agrees not to supply study drug to any person except to those subjects enrolled in the study. Upon termination of the study, all used and unused study drug and remaining materials supplied by Auxilium will be returned for destruction as instructed by the clinical monitor.

7.11. Treatment

Subjects may receive up to a maximum of 3 injections of study drug. Each injection will be separated by a minimum of 21 days.

Subjects will receive Injection 1 on Day 1 of the study. Administration of subsequent injections (ie, Injection 2, Injection 3) will be determined by the guidelines outlined in Table 2:

- Do not retreat: Subjects who meet all criteria for ‘do not retreat’ after Injection 1 or Injection 2 will not receive subsequent injection(s).
- Retreat: Subjects who meet all the criteria for ‘retreat’ after Injection 1 or Injection 2 will be eligible to receive subsequent injection(s) provided there are no safety issues (eg, adverse events; allergic reaction), as determined by the investigator.
- Investigator-Discretion: Subjects who do not meet the criteria for ‘do not retreat’ or ‘retreat’ after Injection 1 or Injection 2, will receive additional treatment at the discretion of investigator.

Table 2: Guidelines for Retreatment of Affected Shoulder

	Do Not Retreat^a	Retreat^b
Forward flexion:		
Active (sitting)	≥160°	<140°
Passive (supine)	≥160°	<140°
Abduction:		
Active (sitting)	≥160°	<140°
Passive (supine)	≥160°	<140°
External rotation with the elbow up to 90° abduction:		
Active (sitting)	≥45°	<30°
Passive (supine)	≥45°	<30°
Internal rotation with the elbow up to 90° abduction:		
Active (sitting)	≥45°	<30°
Passive (supine)	≥45°	<30°
^a Do not retreat if all measurements criteria are met. ^b Retreat if all measurement criteria are met and if the investigator determines there are no safety issues (eg, ongoing adverse events).		
IF NEITHER THE CRITERIA FOR 'DO NOT RETREAT' OR 'RETREAT' ARE MET AFTER INJECTION 1 OR INJECTION 2, THEN ADDITIONAL TREATMENT WILL BE AT THE DISCRETION OF INVESTIGATOR.		

7.11.1. Subjects Not Eligible for Injection 2 and/or Injection 3

Subjects who are not eligible for Injection 2 and/or Injection 3 (eg, successfully treated or ongoing adverse events) will have follow-up visits on Day 43 (Section 7.13.5) and Day 64 (Section 7.13.7). Subjects who are not eligible for Injection 2 and/or Injection 3 will not be required to have a study visit on Day 29 and/or Day 50, respectively. Subjects who are not eligible for Injection 2 because of ongoing adverse events may receive Injection 3 at the discretion of the investigator.

All subjects will have a final follow-up visit on Day 95.

7.12. Drug Accountability

Auxilium or its agent will maintain a master log of kits dispensed to the investigative sites. A drug inventory form must be kept current by the study designated reconstitution person and must be made available to the clinical monitor, Auxilium employees, IRB/IEC, and regulatory agencies for routine inspection and accountability during monitoring visits. When instructed by Auxilium Pharmaceuticals, Inc., the investigator agrees to return all original containers of unused study drug to Auxilium Pharmaceuticals, Inc. or their designee.

7.13. Assessments by Visit

7.13.1. Informed Consent

Signed and dated informed consent will be obtained from each subject before any study procedures are undertaken. Details about how the informed consent will be obtained and documented are provided in Section 11.3, Subject Information and Consent.

7.13.2. Screening Period (Day -28 to Day -1)

Subjects meeting the relevant eligibility criteria listed in Section 6 may be enrolled in the study after the nature and purpose of the protocol have been explained and written informed consent to participate has been voluntarily provided by the subject. All subjects will have a screening evaluation within 28 days before their initial injection. The following procedures will be performed and documented during the screening period:

1. Obtain written informed consent, if subject not already consented
2. Medical history including adhesive capsulitis (AC) history (Section 7.14)
3. Record prior and concomitant medications/procedures (Section 7.14.2)
4. Physical examination (Section 7.14.3)
5. Vital sign measurements (Section 7.14.7)
6. Targeted examination of the shoulders including:
 - Inspection, signs of instability, signs of impingement (affected and unaffected shoulders)
 - AROM and PROM (affected and unaffected shoulders) (Section 7.14.4.2)
 - ASES function sub-scale (affected shoulder) (Section 7.14.4.3)
 - ASES pain sub-scale (affected shoulder) (Section 7.14.4.3)
 - Pain on movement (affected shoulder) (Section 7.14.5)
7. 12-lead electrocardiogram (ECG) (Section 7.14.8)
8. X-ray of affected shoulder (Section 7.14.9)

9. Magnetic resonance imaging (MRI) of the affected shoulder (Section 7.14.9)
10. Collection of samples for:
 - a. Clinical laboratory testing (Section 7.14.10.1)
 - b. Urine pregnancy testing
 - c. Anti-AUX-I and anti-AUX-II antibody testing and neutralizing antibodies to AUX-I and AUX-II (Section 7.14.10.2)
11. Adverse events (Section 8)

7.13.3. Injection 1 (Day 1)

7.13.3.1. Before Injection

1. Record concomitant medications/procedures (Section 7.14.2)
2. Vital sign measurements (Section 7.14.7)
3. Targeted examination of the affected shoulder including:
 - AROM and PROM (Section 7.14.4.2)
4. Urine pregnancy testing
5. Randomization
6. Adverse events (Section 8)

Subjects will receive study drug under ultrasound guidance after administration of local anesthesia (Section 7.6).

7.13.3.2. After Injection

1. Record concomitant medications/procedures (Section 7.14.2)
2. Vital sign measurements (Section 7.14.7)
3. Examination of the affected shoulder for injection site reactions and local tolerability
4. Adverse events (Section 8)

Before discharge, subjects will be given instructions for home shoulder exercises (Section 7.14.6).

7.13.4. Day 8

The following procedures will be performed on Day 8:

1. Record concomitant medications/procedures (Section 7.14.2)
2. Vital sign measurements (Section 7.14.7)

3. Examination of affected shoulder including:
 - AROM and PROM (Section 7.14.4.2)
4. Compliance with home shoulder exercises
5. Injection site reactions and local tolerability
6. Adverse events (Section 8)

